1.0 Skin Toxicities	
	For mucous membrane involvement of SJS or TEN, appropriate consulting services should be offered to guide management in preventing sequelae from scarring (e.g, ophthalmology; ear, nose, and throat; urology; gynecology; etc, as appropriate)
G4: Skin erythema and blistering/sloughing covering $\geq 10\%$ to $> 30\%$ BSA with associated signs (e.g, erythema, purpura, epidermal detachment, mucous membrane detachment) and/or systemic symptoms and concerning associated blood work abnormalities (e.g, liver function test elevations in the setting of DRESS/DIHS)	
Permanently discontinue ICPI
 
Admit patient immediately to a burn unit or ICU with consulted dermatology and wound care services
 
Consider further consultations based on management of mucosal surfaces (e.g, ophthalmology; urology; gynecology; ear, nose, and throat surgery; etc) Initiate IV (methyl)prednisolone (or equivalent) 1-2 mg/kg, tapering when toxicity resolves to normal
 
IVIG or cyclosporine may also be considered in severe or corticosteroid-unresponsive cases
 
Consider pain/palliative consultation and/or admission in patients presenting with DRESS manifestations

Additional considerations: The usual prohibition of corticosteroids for SJS is not relevant here, as the underlying mechanism is a T-cell immunodirected toxicity
 
Adequate suppression is necessary with corticosteroids or other agents and may be prolonged in cases of DRESS/DIHS
 
All recommendations are expert consensus based, with benefits outweighing harms, and strength of recommendations are moderate
	

Abbreviations: ADL, activities of daily living; AE, adverse event; BSA, body surface area; CBC, complete blood count; CTCAE, Common Terminology Criteria for Adverse Events; DIHS, drug-induced hypersensitivity syndrome; DRESS, drug reaction with eosinophilia and systemic symptoms; G, Grade; ICPI, immune checkpoint inhibitor; ICU, intensive care unit; irAE, immune-related adverse event; IV, intravenous; IVIG, intravenous immunoglobulin; NA, not applicable; SCAR, severe cutaneous adverse reactions; SJS, Stevens-Johnson syndrome; TEN, toxic epidermal necrolysis.

Table A2

Management of GI irAEs in Patients Treated With ICPis

2.0 GI Toxicities	
2.1 Colitis	
Definition: A disorder characterized by inflammation of the colon	
Diagnostic work-up	
G2	
Work-up of blood (CBC, comprehensive metabolic panel, TSH, ESR, CRP), stool (culture, Clostridium difficile, parasite, CMV or other viral etiology, ova and parasite) should be performed
 
Consider testing for lactoferrin (for patient stratification to determine who needs more urgent endoscopy) and calprotectin (to follow-up on disease activity)
 
Screening laboratories (HIV, hepatitis A and B, and blood quantiferon for TB) to prepare patients to start infliximab should be routinely done in patients at high risk for those infections and appropriately selected patients based on infectious disease expert's evaluation
 
Imaging (e.g, CT scan of abdomen and pelvis and GI endoscopy with biopsy) should be considered as there is evidence showing that the presence of ulceration in the colon can predict a corticosteroid-refractory course, which may require early infliximab
 
Consider repeating endoscopy for patients who do not respond to immunosuppressive agents; repeating endoscopy for disease monitoring can be considered when clinically indicated and when planning to resume therapy

G3-4	
All the work-up listed for G2 (blood, stool, imaging, and scope with biopsy) should be completed immediately
 
Consider repeating endoscopy for patients who do not respond to immunosuppressive agents; repeating endoscopy for disease monitoring should only be considered when clinically indicated and when planning to resume ICPi

Grading (based on CTCAE for diarrhea, as most often used clinically)	Management
All patients	
Counsel all patients to be aware of and inform their health care provider immediately if they experience: Abdominal pain, nausea, cramping, blood or mucus in stool or changes in bowel habits, fever, abdominal distention, obstipation, constipation
 
For G2 or higher, consider permanently discontinuing CTLA-4 agents and may restart PD-1, PD-L1 agents if patient can recover to G1 or less; concurrent immunosuppressant maintenance therapy should be considered only if clinically indicated in individual cases

G1: Increase of fewer than four stools per day over baseline; mild increase in ostomy output compared with baseline	
Continue ICPi; alternatively, ICPi may be held temporarily and resumed if toxicity does not exceed G1
 
Monitor for dehydration and recommend dietary changes Facilitate expedited phone contact with patient/caregiver May obtain gastroenterology consult for prolonged G1 cases

G2: Increase of four to six stools per day over baseline; moderate increase in ostomy output compared with baseline	
Should hold ICPi temporarily until patient's symptoms recover to G1; can consider permanently discontinuing CTLA-4 agents and may restart PD-1, PD-L1 agents if patient can recover to G1 or less
 
Concurrent immunosuppressant maintenance therapy (10 mg prednisone equivalent dose) may be offered only if clinically indicated in individual cases
 
May also include supportive care with medications such as Imodium if infection has been ruled out
 
Should consult with gastroenterology for G2 or higher

2.0 GI Toxicities	
	
Administer corticosteroids, unless diarrhea is transient, starting with initial dose of 1 mg/kg/day prednisone or equivalent
 
When symptoms improve to G1 or less, taper corticosteroids over at least 4-6 weeks before resuming treatment, although resuming treatment while on low-dose corticosteroid may also be an option after an evaluation of the risks and benefits
 
EGD/colonoscopy, endoscopy evaluation should be highly recommended for cases Grade ≥ 2 to stratify patients for early treatment with infliximab based on the endoscopic findings and to determine the safety of resuming PD-1, PD-L1 therapy
 
Stool inflammatory markers can be considered (lactoferrin and calprotectin) in cases of G2 or higher to differentiate functional versus inflammatory diarrhea, and use calprotectin to monitor treatment response if provider prefers
 
Repeat colonoscopy is optional for cases of G2 or higher for disease activity monitoring to achieve complete remission, especially if there is a plan to resume ICPi

G3: Increase of seven or more stools per day over baseline, incontinence, hospitalization indicated, severe increase in ostomy output compared with baseline, limiting self-care ADL	
Should consider permanently discontinuing CTLA-4 agents and may restart PD-1, PD-L1 agents if patient can recover to G1 or less.
 
Administer corticosteroids (initial dose of 1-2 mg/kg/d prednisone or equivalent)
 
Consider hospitalization or outpatient facility for patients with dehydration or electrolyte imbalance
 
If symptoms persist ≥ 3-5 days or recur after improvement, consider administering IV corticosteroid or noncorticosteroid (e.g, infliximab)
 
Consider colonoscopy in cases where patients have been on immunosuppression and may be at risk for opportunistic infections as an independent cause for diarrhea (i.e, CMV colitis) and for those who are anti-TNF or corticosteroid refractory

G4: Life-threatening consequences; urgent intervention indicated	
Permanently discontinue treatment
 
Should admit patient when clinically indicated; patients managed as outpatients should be very closely monitored
 
Administer 1-2 mg/kg/d methylprednisolone or equivalent until symptoms improve to G1, and then start taper over 4-6 weeks
 
Consider early infliximab 5-10 mg/kg if symptoms refractory to corticosteroid within 2-3 days Consider lower GI endoscopy if symptoms are refractory despite treatment or there is concern of new infections

Additional considerations
 
The use of vedolizumab may be considered in patients refractory to infliximab and/or contraindicated to TNF-a blocker. The decision should be made on an individual basis from gastroenterology and oncology evaluation. This is based on case series showing promising results
 
Patients with hepatitis and irAE colitis are rare, and management should include permanently discontinuing ICPi and offering other immunosuppressant agents that work systemically for both conditions
	

2.0 GI Toxicities	
Currently, enteritis alone as the cause of diarrhea is uncommon and requires small bowel biopsy as the evaluation tool. It may be managed similar as colitis, including corticosteroid and/or infliximab, etc	
2.2 Hepatitis	
Definition: A disorder characterized by a viral pathologic process involving the liver parenchyma Diagnostic work-up Monitor patient for abnormal liver blood tests: AST, ALT, and bilirubin prior to each infusion and/or weekly if G1 liver function test elevations. No treatment is recommended for G1 liver function test abnormality For G2 or higher: Work-up for other causes of elevated liver enzymes should be tested, viral hepatitis, alcohol history, iron study, thromboembolic event, liver ultrasound, cross-sectional imaging for potential liver metastasis from primary malignancy. If suspicion for primary autoimmune hepatitis is high, can consider ANAs, antismooth muscle antibodies, antineutrophil cytoplasmic antibodies. If patients with elevated alkaline phosphatase alone, g-glutamyl transferase should be tested. For isolated elevation of transaminases, consider checking CK for other etiologies	
Grading	Management
All patients	Counsel all patients to be aware of and inform their health care provider immediately if they experience: Yellowing of skin or whites of the eyes Severe nausea or vomiting Pain on the right side of the abdomen Drowsiness Dark urine (tea colored) Bleeding or bruising more easily than normal Feeling less hungry than usual
G1: Asymptomatic (AST or ALT > ULN to 3.0 x ULN and/or total bilirubin > ULN to 1.5 x ULN)	Continue ICPi with close monitoring; consider alternate etiologies Monitor laboratories one to two times weekly Manage with supportive care for symptom control
G2: Asymptomatic (AST or ALT > 3.0 to \leq 5 x ULN and/or total bilirubin > 1.5 to \leq 3 x ULN)	Hold ICPi temporarily and resume if recover to G1 or less on prednisone \leq 10 mg/d For Grade 2 hepatic toxicity with symptoms, may administer corticosteroid 0.5-1 mg/kg/d prednisone or equivalent if the abnormal elevation persists with significant clinical symptoms in 3-5 days Increase frequency of monitoring to every 3 days Infliximab might not be the most appropriate treatment option in the situation of immune-mediated hepatitis given the potential risk of idiosyncratic liver failure (Note: No clear evidence shows the liver toxicity from infliximab from other studies) In follow-up, may resume ICPi treatment followed by taper only when symptoms improve to G1 or less and corticosteroid \leq 10 mg/d; taper over at least 1 month Patients should be advised to stop unnecessary medications and any known hepatotoxic drugs
G3: Symptomatic liver dysfunction, fibrosis by biopsy, compensated cirrhosis, reactivation of chronic hepatitis (AST or ALT 5-20 x ULN and/or total bilirubin 3-10x3 ULN)	Permanently discontinue ICPi Immediately start corticosteroid 1-2 mg/kg methylprednisolone or equivalent If corticosteroid refractory or no improvement after 3 days, consider mycophenolate mofetil or azathioprine (if using azathioprine should test for thiopurine methyltransferase deficiency) Laboratories at daily or every other day; consider inpatient monitoring for patients with AST/ALT > 8 x ULN and/or elevated TB 3 x ULN

2.0 GI Toxicities	
	
Increase frequency of monitoring to every 1-2 days
 
Infliximab might not be the most appropriate treatment option in the situation of immune-mediated hepatitis given the potential risk of liver failure (Note: No clear evidence shows that the liver toxicity from infliximab from other studies); alternatives include non-TNF-α agents as systemic immunosuppressants If no improvement is achieved with corticosteroids or for patients on combination therapy with a novel agent, with standard chemotherapy, or with targeted therapy, refer to hepatologist for further pathologic evaluation of hepatitis
 
Corticosteroid taper can be attempted around 4-6 weeks; re-escalate if needed; optimal duration unclear

G4: Decompensated liver function (e.g, ascites, coagulopathy, encephalopathy, coma; AST or ALT > 20 x ULN and/or total bilirubin > 10 x ULN)	
Permanently discontinue ICPi
 
Administer 2 mg/kg/d methylprednisolone equivalents
 
If corticosteroid refractory or no improvement after 3 days, consider mycophenolate mofetil
 
Monitor laboratories daily; consider inpatient monitoring
 
Avoid the use of infliximab in the situation of immune-mediated hepatitis
 
Hepatology consult if no improvement was achieved with corticosteroid
 
Corticosteroid taper can be attempted around 4-6 weeks when symptoms improve to G1 or less; re-escalate if needed; optimal duration unclear
 
Consider transfer to tertiary care facility if necessary

All recommendations are expert consensus based, with benefits outweighing harms, and strength of recommendations is moderate.	

Abbreviations: ADL, activities of daily living; ALT, alanine aminotransferase; ANA, antinuclear antibody; AST, aspartate aminotransferase; CBC, complete blood count, CK, creatine kinase; CMV, cytomegalovirus; CRP, C-reactive protein; CT, computed tomography; CTCAE, Common Terminology Criteria for Adverse Events; CTLA-4, cytotoxic T-cell lymphocyte-associated antigen-4; EGD, esophagogastroduodenoscopy; ESR, erythrocyte sedimentation rate; G, Grade; GI, gastrointestinal; HIV, human immunodeficiency virus; ICPi, immune checkpoint inhibitor; irAE, immune-related adverse event; IV, intravenous; PD-1; programmed death 1; PD-L1, programmed death-ligand 1; TB, tuberculosis; TNF, tumor necrosis factor; TSH, thyroid-stimulating hormone; ULN, upper limit of normal.

Table A3

Management of Lung irAEs in Patients Treated With ICPis

3.0 Lung Toxicities	
3.1 Pneumonitis	

Definition: Focal or diffuse inflammation of the lung parenchyma (typically identified on CT imaging)
 
No symptomatic, pathologic, or radiographic features are pathognomonic for pneumonitis
 
Diagnostic work-up
 
Should include the following: CXR, CT, pulse oximetry
 
For G2 or higher, may include the following infectious work-up: nasal swab, sputum culture and sensitivity, blood culture and sensitivity, urine culture and sensitivity
	
Grading	Management
G1: Asymptomatic, confined to one lobe of the lung or < 25% of lung parenchyma, clinical or diagnostic observations only	
Continue ICPi
 
If clinically indicated. Monitor participants weekly or more frequently as needed with history, physical examination and pulse oximetry; may also offer CXR. May offer one repeat CT scan in 3-4 weeks; in patients who have had baseline testing, may offer a repeat spirometry/DLCO in 3-4 weeks
 
If symptoms appear and/or changes in the physical exam are noted, treat as G2

G2: Symptomatic, involves more than one lobe of the lung or 25%-50% of lung parenchyma, medical intervention indicated, limiting instrumental ADL	
Hold ICPi until resolution to G1 or less
 
Prednisone 1-2 mg/kg/d and taper by 5-10 mg/wk over 4-6 weeks Consider bronchoscopy with BAL
 
Consider empirical antibiotics
 
Monitor every 3 days with history and physical examination and pulse oximetry, consider CXR; no clinical improvement after 48-72 hours of prednisone, treat as G3

G3: Severe symptoms, hospitalization required, involves all lung lobes or 50% of lung parenchyma, limiting self-care ADL, oxygen indicated G4: Life-threatening respiratory compromise, urgent intervention indicated (intubation)	
Permanently discontinue ICPi
 
Empirical antibiotics; (methyl)prednisolone IV 1-2 mg/kg/d; no improvement after 48 hours, may add infliximab 5 mg/kg or mycophenolate mofetil IV 1 g twice a day or IVIG for 5 days or cyclophosphamide; taper corticosteroids over 4-6 weeks
 
Pulmonary and infectious disease consults if necessary
 
Bronchoscopy with BAL ± transbronchial biopsy
 
Patients should be hospitalized for further management


Additional considerations
 
GI and Pneumocystis prophylaxis with PPI and Bactrim may be offered to patients on prolonged corticosteroid use (> 12 weeks), according to institutional guidelines
 
Consider calcium and vitamin D supplementation with prolonged corticosteroid use
 
The role of prophylactic fluconazole with prolonged corticosteroid use (> 12 weeks) remains unclear, and physicians should proceed according to institutional guidelines
 
Bronchoscopy + biopsy; if clinical picture is consistent with pneumonitis, no need for biopsy
 
All recommendations are expert consensus based, with benefits outweighing harms, and strength of recommendations are moderate.
	

Abbreviations: ADL, activities of daily living; BAL, bronchoalveolar lavage; CT, computed tomography; CXR, chest X-ray; DLCO, diffusing capacity of lung for carbon monoxide; G, Grade; GI, gastrointestinal; ICPi, immune checkpoint inhibitor; irAE, immune-related adverse event; IV, intravenous; IVIG, intravenous immunoglobulin; PPI, proton pump inhibitor.

Table A4

Management of Endocrine irAEs in Patients Treated With ICPis

4.0 Endocrine Toxicity	
Counsel patients to inform their health care provider immediately if they experience any changes in their health since their last visit, especially any of the following:	
Headaches that will not go away or unusual headache patterns Vision changes Rapid heartbeat Increased sweating Extreme tiredness or weakness Muscle aches Weight gain or weight loss Dizziness or fainting Feeling more hungry or thirsty than usual Hair loss Changes in mood or behavior, such as decreased sex drive, irritability, or forgetfulness Feeling cold Constipation Voice gets deeper Urinating more often than usual Nausea or vomiting Abdominal pain	
4.1 Thyroid	
4.1.1 Primary hypothyroidism	
Definition: Elevated TSH, normal or low FT4 Diagnostic work-up TSH and FT4 every 4-6 weeks as part of routine clinical monitoring on therapy or for case detection in symptomatic patients	
Grading	Management
G1: TSH < 10 mIU/L and asymptomatic G2: Moderate symptoms; able to perform ADL; TSH persistently > 10 mIU/L	Should continue ICPi with close follow-up and monitoring of TSH, FT4 May hold ICPi until symptoms resolve to baseline Consider endocrine consultation Prescribe thyroid hormone supplementation in symptomatic patients with any degree of TSH elevation or in asymptomatic patients with TSH levels that persist > 10 mIU/L (measured 4 weeks apart) Monitor TSH every 6-8 weeks while titrating hormone replacement to normal TSH FT4 can be used in the short term (2 weeks) to ensure adequacy of therapy in those with frank hypothyroidism where the FT4 was initially low Once adequately treated, should monitor thyroid function (at least TSH) every 6 weeks while on active ICPi therapy or as needed for symptoms to ensure appropriate replacement; repeat testing annually or as indicated by symptoms once stable
G3-4: Severe symptoms, medically significant or life-threatening consequences, unable to perform ADL	Hold ICPi until symptoms resolve to baseline with appropriate supplementation Endocrine consultation

4.0 Endocrine Toxicity	
	May admit for IV therapy if signs of myxedema (bradycardia, hypothermia) Thyroid supplementation and reassessment as in G2

Additional considerations
 
For patients without risk factors, full replacement can be estimated with an ideal body weight-based dose of approximately 1.6 µg/kg/d
 
For elderly or fragile patients with multiple comorbidities, consider titrating up from low dose, starting at 25-50 mg
 
Extreme elevations of TSH can be seen in the recovery phase of thyroiditis and can be watched in asymptomatic patients to determine whether there is recovery to normal within 3-4 weeks
 
Under guidance of endocrinology, consider tapering hormone replacement and retesting in patients with a history of thyroiditis (initial thyrotoxic phase)
 
Adrenal dysfunction, if present, must always be replaced before thyroid hormone therapy is initiated
	

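### Two adjacent lines on thyroid-hormone replacement in Protocol Appendix 5 contradict each other: the low starting dose, as printed, is hundreds of times the full dose

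*Protocol*

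**What the plan says.** Protocol Appendix 5 gives investigators recommendations for managing immune-related adverse events. Table A4 covers endocrine events, and its subsection 4.1.1 covers primary hypothyroidism. The management column there says: "Prescribe thyroid hormone supplementation in symptomatic patients with any degree of TSH elevation". This is the only agent in 4.1.1 to which a replacement dose can refer.

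The additional considerations at the end of 4.1.1 then give two doses in consecutive lines. For patients without risk factors, "full replacement can be estimated with an ideal body weight-based dose of approximately 1.6 µg/kg/d". The next line reads: "For elderly or fragile patients with multiple comorbidities, consider titrating up from low dose, starting at 25-50 mg".

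No other part of the protocol gives a thyroid-hormone dose, and the SAP gives none, so nothing elsewhere reconciles the two lines.

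Sites are directed to this table. Protocol 2.3 and 6.9.2 list immune-related thyroid disorders among the important identified risks of the study drug. Sections 6.8 and 6.9.2 refer investigators to Appendix 5 for specific immune-related events. The Schedule of Activities has free T4 and TSH tested every 6 weeks on treatment.

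**The concern.** A starting dose described as low, to be titrated upward, should lie below full replacement. Here the full dose is in micrograms per kilogram and the starting dose is in milligrams, with no time unit. Taken as printed, the order of the two is reversed by a factor in the hundreds.

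What is at stake is the safety of participants, not inference. The second line is addressed to elderly or fragile patients with comorbidities. Such participants are not ruled out: inclusion criterion 1 sets no upper age limit, and SAP 11.1 has age categories up to 85 years and over. Guidance that sites are sent to for an identified risk of the study drug should not contain two doses that cannot both stand.

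**Working it through.** The documents state no ratio of their own, so there is no figure to reproduce. The check is a unit conversion followed by a division.

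**Inputs from Appendix 5, Table A4, 4.1.1**
- Full replacement: 1.6 µg per kg ideal body weight per day.
- Low starting dose as printed: 25 to 50 mg, which is 25,000 to 50,000 µg.

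**Assumptions, because the documents are silent**
- The 25 to 50 mg is a daily dose.
- Ideal body weight is 70 kg for the central case, varied from 40 to 100 kg.

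**Formula**

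Ratio = starting dose in µg / (1.6 × weight in kg)

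| Assumed ideal body weight | Full dose per day | 25 mg ÷ full dose | 50 mg ÷ full dose |
|---|---|---|---|
| 40 kg | 64 µg | 391 | 781 |
| 50 kg | 80 µg | 313 | 625 |
| 60 kg | 96 µg | 260 | 521 |
| 70 kg | 112 µg | 223 | 446 |
| 80 kg | 128 µg | 195 | 391 |
| 90 kg | 144 µg | 174 | 347 |
| 100 kg | 160 µg | 156 | 313 |

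**Does any weight remove the conflict?** Setting 25,000 = 1.6 × weight gives 25,000 / 1.6 = 15,625 kg. Below that weight the printed starting dose exceeds full replacement.

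**Does the daily reading matter?** If the 25 to 50 mg were spread over a week, the 70 kg ratios would be 223 / 7 ≈ 32 and 446 / 7 ≈ 64. The size changes, but the contradiction does not.

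**The case against.** The strongest objection is that the unit may come from the reading of the PDF. Greek letters elsewhere in Appendix 5 appear as Latin look-alikes: TNF-a in 2.1 (Colitis), g-glutamyl in 2.2 (Hepatitis) and b-Blocker in 4.1.2 (Hyperthyroidism), the subsection that follows this one. A Greek mu turned into m would make micrograms look exactly like milligrams. Against this, the µg in the line directly above is read correctly, as are TNF-α in 2.2 and β-blockers in 7.1 (Myasthenia gravis). The handling is therefore inconsistent and the extracted text cannot settle the question. This part of the objection stands: the page itself must be checked, and if it prints micrograms the point falls away.

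The second objection concerns consequences. A reader might infer that the line will be followed, that participants will be harmed, and that the resulting events will enter the trial's safety results. The documents do not show this. They give no frequency for thyroid events. Eligibility requires ECOG 0 to 1 and adequate organ function (inclusion criteria 6 and 8), and exclusion criterion 10 keeps out severe disease that might impair tolerance, so few participants may fit the description. The appendix offers recommendations and the line itself only asks the prescriber to consider the dose. Endocrine consultation is to be considered at Grade 2 and is listed at Grades 3 to 4, and 6.9.2 also points to the current NCCN guideline. These safeguards make use of the printed figure less likely; they do not make the two lines agree.

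Third, SAP 4.1 records that the study is being discontinued early with a low number of participants. That limits how far a site notice would reach, but the text still needs correcting.

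**Conclusion.** The contradiction holds for the text as extracted, subject to the check of the PDF page. At an assumed 70 kg, and reading the second figure as daily, the low starting dose is 223 to 446 times the full dose. Over 40 to 100 kg it is about 156 to 781 times. The exact multiple rests on those two assumptions. The existence of the conflict does not, since no adult weight brings the printed starting dose down to the full dose.

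A reader might also infer that the milligram line is the wrong one and what it should say. The documents establish only that the two lines disagree. This review takes no view on which dose or unit is right.

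The point concerns participant safety. It leaves every endpoint, the sample size and all planned analyses unchanged.

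**What to change.** 1. Look at the PDF page of Table A4, 4.1.1 and confirm the unit printed in each line. Appendix 5 says that FDA-recommended departures from the ASCO/NCCN guidance are in bold and underlined, so the page will also show whether either line is marked as one.
2. If the conflict is on the page, have the sponsor reconcile both lines against the source guideline and amend the table, stating the unit and the time basis in each line.
3. Tell any site that still has participants under treatment or follow-up, allowing for the early discontinuation recorded in SAP 4.1.
4. Correct the text before Appendix 5 is reused in another protocol.

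The cost is one table entry and, where participants remain, a short notice to sites. There is no design or analysis cost.
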